8.3 Exploratory Endpoint

8.3.1 Exploratory Endpoint Analyses

The CDAI score and PRO-2 score will be evaluated at baseline and at Weeks 2, 4, 6, 8, 10, and 12 in this trial, so that the by-visit analysis of CDAI remission and PRO-2 remission (exploratory endpoints #1 and #2) at Weeks 2, 4, 6, 8, and 10, in addition to Week 12, will be provided and analyzed using a similar method with Week 12 replaced by Weeks 2, 4, 6, 8 or 10. Since the by-visit analysis of an endpoint is considered as supplemental to the analysis of the endpoint at Week 12, no adjustment in alpha is necessary.

Additional exploratory endpoints are as follows:

- 3) The percentage of subjects with a biological response in subjects with elevated levels of CRP, defined as a reduction in the level of CRP to within the normal range or by at least 15%, at Week 6, Week 12, and at the 30-day follow-up.
- 4) The percentage of subjects with a biological response in subjects with elevated levels of FCP, defined as a reduction in the level of FCP to within the normal range or by at least 15%, at Week 6, Week 12, and at the 30-day follow-up.
- 5) Characterization of the fecal microbiota profile and abundance based on taxonomic and functional annotation from next-generation sequencing, change from baseline, and association with phenotype, at Week 2, Week 12, and at the 30-day follow-up.

CMH test stratified by the randomization stratification factors will be applied to the exploratory endpoint #3 and #4. The mean change from baseline will be provided by visit for the additional exploratory endpoints#5. An analysis of covariance (ANCOVA) with baseline value as covariate and treatment as main effects will be applied to this endpoint.

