3.5.3 Exploratory Endpoints

The exploratory endpoints are as follows:

- 1) By-visit analysis of CDAI remission (defined as a CDAI score < 150).
- 2) By-visit analysis of PRO-2 remission (defined as stool frequency \leq 3 times per day and abdominal pain \leq 1).
- 3) The percentage of subjects with a biological response in subjects with elevated levels of C-reactive protein (CRP), defined as a reduction in the level of CRP to

Protocol 341-201-00004

within the normal range or by at least 15%, at Week 6, Week 12, and at the 30-day follow-up.

- 4) The percentage of subjects with a biological response in subjects with elevated levels of fecal calprotectin (FCP), defined as a reduction in the level of FCP to within the normal range or by at least 15%, at Week 6, Week 12, and at the 30-day follow-up.
- 5) Characterization of the fecal microbiota profile and abundance based on taxonomic and functional annotation from next-generation sequencing, change from baseline, and association with phenotype, at Week 2, Week 12, and at the 30-day follow-up.

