3.7.5.2 Pharmacodynamic Assessments

A blood sample will be collected and processed into plasma to assess CRP. If CRP is not elevated on Day 1, there is no need for any further CRP assessments. In addition, a fecal sample will be collected to assess FCP.

No formal pharmacodynamic (PD) assessments are planned.

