6.2 Pharmacodynamic Methods

No PD analysis will be performed.

Protocol 341-201-00004

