CT-12.3 Incidence of Potentially Clinically Relevant Changes in ECG Evaluations

CT-12.4 Mean Change from Baseline in Electrocardiogram Results

CT-13.1 By-visit Analysis of CDAI remission

CT-13.2 By-visit Analysis of PRO-2 remission

CT-13.3 Summary of the Percentage of Subjects with a Biological Response in Subjects with Elevated Levels of CRP

CT-13.4 Summary of the Percentage of Subjects with a Biological Response in Subjects with Elevated Levels of FCP

CT-13.5 Summary of Characterization of the Fecal Microbiota Profile and Abundance Based on Taxonomic and Functional Annotation

CT-14 Regression Analysis of QTC Parameters

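### CRP and FCP are compared between arms only as a yes/no response, so the plan gives no between-arm estimate of the size of effect on either marker

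*SAP*

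**What the plan says.** Exploratory endpoints #3 and #4 (Protocol 3.5.3, SAP 8.3.1) are response percentages among subjects with elevated marker levels, at Week 6, Week 12 and the 30-day follow-up. For CRP, response is "defined as a reduction in the level of CRP to within the normal range or by at least 15" percent; for FCP it is "defined as a reduction in the level of FCP to within the normal range or by at least 15" percent.

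The planned analysis is in SAP 8.3.1: "CMH test stratified by the randomization stratification factors will be applied to the exploratory endpoint #3 and #4". Continuous analysis goes to the microbiota endpoint alone: "The mean change from baseline will be provided by visit for the additional exploratory endpoints#5", followed by "An analysis of covariance (ANCOVA) with baseline value as covariate and treatment as main effects will be applied to this endpoint".

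The table list in SAP Appendix 4 agrees. CT-13.3 is titled "Summary of the Percentage of Subjects with a Biological Response in Subjects with Elevated Levels of CRP", and CT-13.4 is its FCP counterpart. No table of CRP or FCP levels is listed. Protocol 6.2 adds: "No PD analysis will be performed".

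Sampling differs between the markers. For CRP, Protocol 3.7.5.2 says: "If CRP is not elevated on Day 1, there is no need for any further CRP assessments". FCP has no such rule. Table 3.7-1 schedules it for every subject on Day 1, at Week 6, at Week 12 and at follow-up.

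**The concern.** The response rule is easy to meet without a drug effect. Baseline is one Day 1 value, and for CRP that same value decides who is followed. Selecting on a single high reading and measuring change from it builds in regression to the mean. The normalisation route has no minimum fall: a subject 4% above the upper limit who drops 5% ends at 1.04 × 0.95 = 0.988 of the limit and is a responder. The documents do not justify the 15% cut against the variation of either marker.

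At stake is how much can be learned from samples already collected. A proof-of-concept trial with three doses wants effect size and dose ordering. A response percentage with a high placebo rate gives a weak signal on both, and a difference in percentages does not say by how much the marker fell.

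**Working it through.** **Inputs.** From the documents: the 15% cut, the normalisation route, the single Day 1 baseline and the CMH test. They state no expected response rate, power or variability for CRP or FCP, so there is no plan figure to reproduce. Assumed: log-normal markers and a log-scale within-subject SD *s* of 0.10 to 0.6 (a CV of √(exp(s²) − 1), about 10% to 66%).

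**Step 1: 15% route alone, no baseline selection.** The log change between two visits has SD √2·s.
- No true change: P(response) = Φ(ln 0.85 / (√2·s)), with ln 0.85 = −0.1625.
- True 30% reduction (ln 0.70 = −0.3567): P(response) = Φ((−0.1625 + 0.3567) / (√2·s)).

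At s = 0.25, √2·s = 0.354. No change: Φ(−0.460) = 0.323. A 30% reduction: Φ(0.549) = 0.709.

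**Step 2: efficiency for a 30% reduction.** This is the squared standardised difference in proportions divided by that for mean log change. At s = 0.25:
- Binary: (0.709 − 0.323)² / (0.323 × 0.677 + 0.709 × 0.291) = 0.149 / 0.425 = 0.351.
- Continuous: 0.3567² / (2 × 0.354²) = 0.509.
- Ratio: 0.351 / 0.509 = 0.69.

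**Step 3: add baseline selection, regression to the mean and normalisation.** Simulation with an upper limit of 5 units, median 8 or 12 units and between-subject log SD 1.0 or 1.2, comparing the response test with ANCOVA on the log value:

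| Within-subject SD (log) | Respond, no true change | Efficiency vs ANCOVA, 30% reduction |
|---|---|---|
| 0.10-0.15 | 14-25% | loss about 0-23% |
| 0.25 | 35-36% | 0.67 |
| 0.4 | 43-45% | 0.63 |
| 0.6 | 48-51% | 0.59-0.60 |

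A repeat run over 0.25 to 0.6 gave 0.59 to 0.68. With a true 30% reduction, 65-75% respond over that range.

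**Step 4: cross-check for small effects.** A cut met by a proportion p keeps φ(z_p)² / [p(1 − p)] of the information in mean log change. The maximum is 2/π = 0.64 at p = 0.5, so the loss is at least 36%. It is 40% at CV 30% and 37-38% at CV 50-100%. At CV 10-15% this formula gives 61-49%, unlike the 0-23% above, because a 30% shift is then no longer small against the noise. With so little noise either test finds such a shift easily, and I put no weight on the low-SD loss.

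**Step 5: illustration of power.** Assume 30 placebo and 60 pooled-dose subjects elevated at baseline, CV 40% and a true ratio of 0.70. The SD of log change is √(2 ln 1.16) = 0.545. Response rates are Φ(−0.298) = 0.383 and Φ(0.356) = 0.639.
- Log change: 0.3567 / (0.545 × √(1/30 + 1/60)) = 2.93, and Φ(2.93 − 1.96) gives 83% power.
- Binary: null SE √(0.554 × 0.446 × (1/30 + 1/60)) = 0.111, alternative SE 0.108, and Φ((0.256 − 1.96 × 0.111) / 0.108) gives about 64% power.

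**The case against.** The strongest reply is that little depends on this.

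- **Exploratory status.** The endpoints lie outside the gatekeeping of SAP 8.4, and SAP Section 11 records that the planned analyses will not be performed because only three subjects were randomised. This stands and sets the severity.
- **Inflammation is measured elsewhere.** A reader might infer that the trial gets no estimate of how much OPS-2071 lowers inflammation. The documents do not support that. Change in the Simple Endoscopic Score (SES-CD), from centrally read ileocolonoscopy, is secondary endpoint #2 and is analysed by ANCOVA. What is missing is the size of effect on CRP and FCP. SES-CD is scored only at screening and Week 12, so it does not replace them at Week 6 or follow-up.
- **No bias.** A high response rate without a drug effect might suggest a misleading comparison. Regression to the mean acts alike in all randomised arms. On the assumed figures the endpoint still discriminates, at 35-51% without an effect against 65-75% with a 30% reduction.
- **Generic loss.** Most of the efficiency loss is the usual price of dichotomising, not something peculiar to 15%. That is correct, and a continuous analysis is the answer to it.
- **Laboratory summaries.** SAP 9.3 plans change-from-baseline summaries for central laboratory measurements, and Protocol Table 3.7.3.2-1 lists both markers under additional tests. Appendix 4 names mean-change tables for chemistry, hematology and urinalysis only. Coverage is arguable, and it would be descriptive.
- **Who is available.** It is tempting to say that both markers exist only in an elevated subset of about 60 per arm. The stopping rule covers CRP only, 60 is the whole randomised arm, and the number elevated is not stated.

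**Conclusion.** The point holds as a low-severity improvement. On the text, SAP 8.3.1 compares CRP and FCP between arms only as a dichotomy, and no planned table estimates the size of effect on either marker.

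The numerical cost is conditional. That a third to a half of subjects respond with no true change is not a property of the plan. It needs a within-subject log SD of about 0.25 or more, which the documents do not give, and the rate is well below that at 0.10 to 0.15. The efficiency figures also rest on log-normal data, a uniform proportional shift and complete follow-up. What is lost is power and a readable effect size.

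**What to change.** In SAP 8.3.1, add for each marker an ANCOVA of the log value at Week 6, Week 12 and follow-up, with log Day 1 value, treatment and the randomisation strata. Report geometric mean ratios with 95% confidence intervals for pooled 600 and 300 mg, and for each dose, against placebo. Run it for CRP in subjects elevated on Day 1, and for FCP both in the elevated subset and in all subjects sampled. Keep the 15%-or-normalisation response analysis.

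State how withdrawals, and values after Crohn's medication is increased or added, are handled, in line with the estimand in SAP 5.2 and 8.1.1. A dichotomy can absorb such subjects as nonresponders; a continuous outcome cannot. SAP 5.2 addresses primary and secondary endpoints and SAP 8.3.2 addresses exploratory #1 and #2, so a rule written here would serve #3 and #4 as well.

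The cost is SAP wording, a few extra tables and that missing-data rule. No new samples are needed and no alpha is affected. Because the analyses will not be run in this trial, the change matters for the plan as written and for any reuse of it.

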Eligible subjects will be randomized on Day 1 in a 1:1:1:1 ratio to 1 of 4 treatments: placebo BID, OPS-2071 150 mg BID, OPS-2071 300 mg BID, or OPS-2071 600 mg BID. The randomization will be stratified by CDAI score (CDAI 180 - 300 and CDAI > 300 - 450) and concomitant Crohn's disease medication status (subjects who are treated with anti TNF- α monoclonal antibody, subjects who are treated with low-dose steroids, and subjects who are treated with other Crohn's disease medications). The IMP will be administered twice a day, 8 to 12 hours apart, starting on Day 1 for a total of 12 weeks. Blood samples for PK analysis will be collected throughout the 12 week treatment period according to the schedule of assessments (Table 3.7-1). Efficacy will be assessed using the CDAI, Simple Endoscopic Score for Crohn's Disease (SES-CD), and the two-item patient reported outcome (PRO-2). Definitions of remission and nonremission subjects (ie, treatment failures) can be found in Section 7.4.1. A 30 day (post treatment) follow-up assessment will be performed for all subjects; the CDAI score will be calculated, inflammatory biomarkers and microbiota flora will be checked, and safety measures will be performed. Subjects who increase dosages of baseline Crohn's disease medications or take a new therapy for Crohn's disease during the trial are considered as treatment failures (nonresponders). These subjects are encouraged to stay in the trial for continuous data collections.

A blood sample for future biospecimen research (FBR) will be taken from subjects who consent to the collection of this sample.

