8.1.2 Primary Efficacy Analysis

Logistic regression with terms of treatment group, the randomization stratification factors, location of disease, country, age, sex, disease duration, smoking habit, and baseline CDAI, and baseline CDAI with CDAI stratification factor interaction will be applied to the primary endpoint. The FAS will be used in the efficacy analysis.

The primary analysis of this trial is comparison of the pooled OPS-2071 600 mg BID and 300 mg BID treatment groups with placebo in the primary endpoint of clinical remission.

If this analysis is significant at a 2-sided alpha level of 0.05, comparisons to OPS-2071 600 mg BID versus placebo and OPS-2071 300 mg BID versus placebo in the primary endpoint will be conducted with a 2-sided alpha level of 0.05 in each comparison. If the comparison of the pooled OPS-2071 dose groups versus placebo in the primary endpoint is significant at a 2-sided alpha level of 0.05, and a comparison, say, OPS-2071 600 mg BID versus placebo, is also significant at a 2-sided alpha level of 0.05, the null hypothesis of equal response of OPS-2071 600 mg BID and placebo in the primary endpoint will be considered rejected with an experiment-wise Type I error of 0.05.

The comparison between OPS-2071 150 mg BID versus placebo in the primary endpoint is considered as a secondary analysis and the details are provided in section 8.4.

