8.1.5 Supplemental Analysis

As another sensitivity analysis, the Cochran-Mantel-Haenszel (CMH) test stratified by the randomization stratification factors will be applied to the primary endpoint, and treatment comparisons between individual OPS-2071 dose groups vs. placebo will be conducted.

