8.1.6 Subgroup Analysis

Subgroup analysis of the percentage of subjects who achieve clinical remission at week 12 will be conducted by gender, race (Caucasian and Non-Caucasian), age (18 to < 40, 40 to < 50, and at least 50), and region (US and non-US) using logistic regression with terms of treatment group, the randomization stratification factors, location of disease, disease duration, smoking habit, and baseline CDAI, and baseline CDAI with CDAI stratification factor interaction.

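### The microbiota ANCOVA (exploratory endpoint #5) leaves out the randomisation strata that the SAP's other efficacy comparisons carry; its standard errors are, if anything, slightly too wide

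*SAP*

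**What the plan says.** SAP 3.1 sets a four-arm, equal allocation and states that "The randomization will be stratified by CDAI score" and by concomitant Crohn's medication status. There are two CDAI classes and three medication classes, so six cells.

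For exploratory endpoint #5, characterisation of the fecal microbiota, SAP 8.3.1 gives this model: "An analysis of covariance (ANCOVA) with baseline value as covariate and treatment as main effects will be applied to this endpoint". Just before it, in the same paragraph, the CRP and FCP responder endpoints are handled differently: "CMH test stratified by the randomization stratification factors will be applied to the exploratory endpoint #3 and #4".

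Protocol 7.4.3 leaves the details of the exploratory analyses to the SAP, so the protocol does not supply the missing terms.

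**The concern.** When allocation is balanced within strata, part of the outcome variation that the strata explain is removed from the treatment comparison by design. A model without the strata puts that variation back into the residual, so its standard error does not credit the balance. If CDAI class or background therapy predicts change in the microbiota beyond the subject's own baseline value, the reported intervals are wider than they need be.

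The SAP gives no reason for treating this endpoint differently. Exploratory status does not explain it, because endpoints #3 and #4 are exploratory and stratified. Nor does the choice of ANCOVA, because the SES-CD change analysis is also an ANCOVA and takes its terms from a stratified model. What is at stake is some precision and the consistency of the plan.

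**Working it through.** **Step 1. Which analyses carry the strata?**

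| Analysis | SAP section | Strata |
|---|---|---|
| Primary logistic model | 8.1.2 | Named: "Logistic regression with terms of treatment group, the randomization stratification factors, location of disease, country, age, sex" and further covariates |
| Placebo-based imputation, CDAI and PRO-2 remission | 8.1.4.1, 8.2.1 | By reference to the primary model |
| Supplemental CMH | 8.1.5 | Named: "test stratified by the randomization stratification factors will be applied to the primary endpoint" |
| Subgroups | 8.1.6 | Named: "using logistic regression with terms of treatment group, the randomization stratification factors" |
| Secondary endpoints, including the SES-CD ANCOVA | 8.2.1 | By reference to the stratified models |
| By-visit CDAI and PRO-2 remission | 8.3.1 | By reference (a similar method) |
| CRP and FCP response | 8.3.1 | Named |
| Microbiota ANCOVA | 8.3.1 | **None** |
| QTc-concentration regression (safety) | 9.6 | None named |

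Among the efficacy comparisons, only endpoint #5 lacks the strata.

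**Step 2. Size by formula.** The plan gives no power or variance figure for endpoint #5, so there is nothing to reproduce. Let R² be the share of the variance left after baseline and treatment that the strata explain. This is an assumption.

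- SE ratio, adjusted to unadjusted = √(1 − R²).
- R² = 0: ratio 1, no difference.
- R² = 0.02: √0.98 = 0.990, so the unadjusted SE is 1/0.990 = 1.01 times as large, about 1% too wide.
- R² = 0.10: √0.90 = 0.949, so 1/0.949 = 1.05, about 5% too wide.
- Equivalent sample size = 1/(1 − R²): 1.02 at R² = 0.02 and 1.11 at R² = 0.10.
- Degrees of freedom used: (2 − 1) + (3 − 1) = 3. With 240 subjects, residual degrees of freedom go from 240 − 5 = 235 to 232.

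**Step 3. Check by simulation.** From the SAP: 240 subjects, 60 per arm, 1:1:1:1, six strata. Assumed: permuted blocks of 4 within stratum, unequal stratum sizes, baseline correlation 0.5, outcome SD 1 before stratum and treatment effects are considered. The adjusted model used all six cells (5 degrees of freedom), slightly more than the 3 needed for main effects. There were 4,000 runs for type I error and 2,000 for power at a difference of 0.4 SD.

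| R² | Reported SE without / with strata | Excess width | Type I error without / with | Power without / with |
|---|---|---|---|---|
| 0 | 0.158 / 0.158 | 0% | 0.054 / 0.053 | 71% / 71% |
| 0.05 | 0.158 / 0.154 | 3% | 0.044 / 0.051 | 73% / 75% |
| 0.10 | 0.158 / 0.150 | 5% | 0.042 / 0.051 | 73% / 76% |
| 0.20 | 0.159 / 0.142 | 12% | 0.029 / 0.052 | 73% / 80% |
| 0.30 | 0.159 / 0.132 | 20% | 0.021 / 0.049 | 74% / 84% |

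A hand check agrees. At R² = 0 the SE is √(1 − 0.5²) × √(2/60) = 0.866 × 0.183 = 0.158. At R² = 0.10 it is 0.158 × 0.949 = 0.150. The 0.054 at R² = 0 is within simulation error of 0.05, since √(0.05 × 0.95/4000) = 0.003.

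**Step 4. Where the loss lies.** At R² = 0.10 the unadjusted estimates varied across runs with SD 0.1495 and the adjusted ones with 0.1491. The estimator is about as precise either way, because the allocation already balances the strata. It is the reported SE of the unadjusted model (0.158) that overstates its variability.

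**The case against.** The strongest case against is that this is a legitimate choice with little consequence. Endpoint #5 is exploratory and largely descriptive. It has no hypothesis, alpha or power calculation, and SAP 8.4 confines multiplicity control to the primary and secondary endpoints. Protocol 3.7.6 says the microbiota data will be reported separately. The model already contains the subject's own baseline value, which may absorb much of any influence of disease activity or background therapy, so the further gain could be zero. SAP 8.3.1 also does not say which microbiota variable is analysed, so the gain cannot be assessed for a particular measure. All of this stands and keeps the priority low. It does not explain why this one efficacy model differs from its neighbours, and adding the factors costs almost nothing even when R² is zero.

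A reader might infer three stronger things that the documents do not support:

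- **That the inference is invalid, or the error bars too narrow.** The direction is the opposite: the estimate is essentially unbiased and the test is at or below its nominal level within simulation error.
- **That this is the only between-arm analysis in the SAP without strata.** The placebo-adjusted QTc-concentration regression in SAP 9.6 names none either. The contrast holds for efficacy analyses, and for some of those, including the SES-CD ANCOVA, the strata are inherited by reference and not listed.
- **That precision is certainly lost.** This depends on an R² that the documents do not give.

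**Conclusion.** The point holds as a minor inconsistency with a possible small loss of reported precision. The microbiota ANCOVA omits stratification factors that the other efficacy comparisons include. The standard errors are too wide by 0% if the strata add nothing beyond baseline, and by about 1% to 5% if they explain 2% to 10% of residual variance. The simulated values of 20% and 30% show how the effect would grow; nothing in the documents suggests them. All these sizes rest on assumed R² values, and the simulation also assumes full data on 240 subjects.

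SAP section 11 says the planned analyses will not be performed because only three subjects were randomised. No result is affected. The point matters for the plan as written and for any reuse of its text.

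**What to change.** In SAP 8.3.1, specify for exploratory endpoint #5: ANCOVA with treatment, CDAI stratum and concomitant-medication stratum as factors and baseline value as covariate. If the omission is deliberate, one sentence giving the reason would do instead.

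The cost is a few words and 3 degrees of freedom. Both factors are already recorded for randomisation, so no new data are needed.
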